E2609 tablets of 5-mg, 10-mg and 25-mg dose strengths will be supplied. Placebo tablets to match E2609 will be of identical appearance. Each subject will receive 2 tablets, which when combined will make up the required doses of E2609 (see below) or placebo, to be administered orally QD with food.

- Stage A: 3 doses (5 mg, 15 mg, and 50 mg) of E2609 or placebo (revised per Amendment 01)
- Stage B, MCI/Prodromal Cohort: 3 doses (5 mg, 15 mg, and 50 mg) of E2609 or placebo (revised per Amendment 01)
- Stage B, Mild to Moderate AD Cohort: 2 doses (15 mg and 50 mg) of E2609 or placebo. (revised per Amendment 01)

Duration of Treatment

The maximum duration of a subject's participation in the study will be approximately 2 years, comprising:

- Screening and Baseline Periods (Prerandomization Phase): up to 60 days
(In subjects who have an active infection within 4 weeks of the planned randomization date, the duration of the pre-randomization phase can be extended by up to 4 weeks to allow additional time for resolution of the infection.)
- Treatment Period (Randomization Phase): up to 78 weeks
- Follow-Up Period (Randomization Phase): 12 weeks (post last dose)

Concomitant Drug/Therapy

The following agents are not permitted before randomization (specific timeframes are shown below) and throughout the study until after the last treatment visit (see Appendix 2 for a detailed listing of these agents):

- Anticoagulants (eg, warfarin, digabatin) are not permitted for a period of 5 half-lives or 7 days (whichever is longer) before randomization
- Drugs which may cause QTc prolongation are not permitted for a period of 5 half-lives or 14 days (whichever is longer) before randomization
- Strong CYP3A4 inhibitors are not permitted for a period of 5 half-lives or 14 days (whichever is longer) before randomization
- Live vaccines are not permitted within 3 months before randomization. This does not apply to non-live/inactivated vaccines
- Ig therapy and biologic drugs are not permitted within 6 months before randomization
- Systemic or ocular immunosuppressive or immunomodulatory drugs are not permitted for a period of 5 half-lives or 60 days (whichever is longer) before randomization

Subjects taking AChEIs or memantine must meet the following criteria in order to be included in the primary analyses:

- On a stable dose for 12 weeks before the baseline cognitive assessments at Visit 2
- Remain on a stable dose while on study

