9.1.1 Prerandomization Phase

The Prerandomization Phase includes a Screening Visit and a Baseline Visit. All Screening Visit assessments must be completed and eligibility to progress must be confirmed before any Baseline Visit assessments are performed. All Screening Visit and Baseline Visit assessments must be completed within 50 days and a window of 7 to 10 days is to be observed between the completion of all Baseline Visit assessments and randomization into the study at Visit 3. Thus, the Prerandomization Phase will last for up to 60 days. The series of assessments conducted during this phase will determine eligibility for randomization into the study.

Inclusion criteria are discussed in [Section 9.1](#) and detailed in [Section 9.3.1](#). Before randomization the clinician will provide a judgment on the classification of a subject as either MCI/Prodromal or likely mild to moderate AD. (revised per Amendment 01) This judgment may be discussed and reviewed with the Sponsor or Sponsor's representative, as necessary.

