10. Subjects with hepatic impairment, with total bilirubin greater than 1.5 \times upper limit of normal (ULN) or International Normalized Ratio (INR) greater than 1.7 at Screening or Baseline. Subjects with Gilbert's syndrome need not be excluded.
11. Any contraindications to MRI or PET scanning, including cardiac pacemaker/ defibrillator or ferromagnetic metal implants (eg, in skull; cardiac devices other than those approved as safe for use in MRI scanners). Subjects who require sedation for MRI or PET scanning as per local guidelines need not be excluded.
12. Any contraindications to lumbar puncture (LP) for CSF sampling (eg, lower spinal malformation on physical examination, local spinal infection or other abnormality, including but not limited to obesity)
13. Severe visual or hearing impairment that would prevent the subject from performing psychometric tests accurately
14. History of Ig deficiency or other immunodeficiency disorders (including subjects known to be human immunodeficiency virus positive)
15. Subjects with chronic viral hepatitis
16. A history of tuberculosis (TB). Subjects with no history of TB will be tested for previous TB exposure (eg, positive tuberculin skin test, interferon gamma release assay or other locally accepted tests) and a positive test will be exclusionary.
17. A history of ophthalmic shingles
18. A history of ocular herpes simplex virus (HSV) infection

19. Any live vaccine in the 3 months before randomization.
20. Any active infection within the last 4 weeks prior to randomization. For such cases, the timing of randomization can be extended (up to 4 weeks) to allow the infection to resolve; psychometric tests conducted at Visit 2 (eg, MMSE, CDR) must be repeated.
21. Any chronic inflammatory disease that is not adequately controlled or that requires systemic or ocular immunosuppressive or immunomodulatory therapy. Subjects with:
 - a. Seasonal or perennial allergic rhinitis, asthma or chronic obstructive pulmonary disease where the condition is considered to be stable and adequately controlled by inhaled steroids need not be excluded.
 - b. Hashimoto's thyroiditis but who are stable on thyroid replacement therapy and not on systemic immunosuppressive therapy need not be excluded.
 - c. Cutaneous manifestations of immunological disease that do not require systemic immunosuppressive therapy or systemic immunomodulatory therapy need not be excluded (topical steroid treatment is permitted).

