- a. A study drug discontinuation threshold will be set based on absolute counts of CD4 (T helper cells), CD8 (cytotoxic T cells), or CD19 (B cells). The discontinuation threshold will be set at below the level of the LLN, at a level that represents a greater risk of opportunistic infection in the treated population. For CD4 (T helper cells) the discontinuation threshold is 250 cells/ μ L. For CD8 (cytotoxic T cells) and CD19 (B cells) the discontinuation thresholds are 150 cells/ μ L and 50 cells/ μ L, respectively. Any subject who has CD4 (T helper cells), CD8 (cytotoxic T cells), or CD19 (B cells) absolute counts below the discontinuation threshold as confirmed by a repeat test conducted within 1 week of the initial test will be discontinued from study drug.
- b. Subjects with CD4 (T helper cells), CD8 (cytotoxic T cells), or CD19 (B cells) absolute counts between the LLN and the discontinuation threshold will have lymphocyte subset counts performed on a weekly basis. Subjects with a >33% reduction from baseline in CD4 (T helper cells), CD8 (cytotoxic T cells), or CD19 (B cells) absolute counts will also have lymphocyte subset counts performed on a weekly basis. For these subjects, the decision as to whether the subject remains on study drug or is to be discontinued from study drug will be based upon clinical judgment and will take into account any clinical presentation in addition to the lymphocyte subset counts. These subjects may continue with treatment if there is no clinical evidence of infection. They will be discontinued from study drug if they have infections of a moderate to severe intensity (eg, subjects whose infections are not localized, or are systemically unwell, or who require systemic anti-infective drug treatment).

Table 1 Study Drug Actions for Lymphocyte Subset Absolute Counts

| Lymphocyte subset absolute counts | Action | Decision to continue or discontinue |
|--|---|---|
| CD4 (T helper cells), CD8 (cytotoxic T cells), or CD19 (B cells) absolute counts below discontinuation threshold | Retest within 1 week | If retest performed within 1 week confirms lymphocyte subset counts below the discontinuation threshold, discontinue study drug |

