ADAS-cog₁₄ = Alzheimer's Disease Assessment Scale - Cognitive subscale (14 items), CBB = CogState Brief Battery, CBP = childbearing potential, CDR = Clinical Dementia Rating scale, CSF = cerebrospinal fluid, C-SSRS = Columbia Suicide Severity Rating Scale, ECG = electrocardiogram, ED = Early Discontinuation, FAQ = Functional Assessment Questionnaire (also known as the Functional Activities Questionnaire), Ig = immunoglobulin, ISLT = International Shopping List Task, LP = lumbar puncture, MMSE = Mini Mental State Examination, MRI = magnetic resonance imaging, PBMC = peripheral blood mononuclear cell, PD = pharmacodynamics, PET = positron emission tomography, PK = pharmacokinetics, UNS = unscheduled.

- a: Visit 3 should be conducted 7 to 10 days after completion of the Baseline visit (Visit 2) assessments and confirmation of eligibility to continue in the study, unless additional time is required to take Exclusion Criterion #19 into account. A window of ± 3 days will be permitted for Visit 4 to 14 inclusive. A window of ± 10 days will be permitted for Visit 15 to 18 inclusive. A window of ± 3 days will be permitted for the Follow-Up Visits. If use is made of the permitted visit windows, every effort should be made to bring the subject back in line with the "weeks elapsed since first dose" at subsequent visits.
- b: Subjects who discontinue taking study drug prematurely for any reason will undergo an ED Visit within 7 days of their last dose of study drug. In addition, Follow-Up Visits will be scheduled 4 and 12 weeks after the last dose of study drug (Visit 19 and Visit 20, respectively). Subjects who discontinue study drug prematurely will also be scheduled to return to the study site for each scheduled visit when clinical efficacy assessments are to be conducted (ie. at Visits 11, 14, 15, 16, 17, and 18, if these visits have not already been performed). At these visits, only clinical efficacy assessments (MMSE, CDR, ADAS-cog₁₄, FAQ, CBB, and ISLT) will be conducted. Regularly scheduled clinical efficacy visits do not need to be attended if they fall within 8 days (visit window) after the Early Discontinuation Visit or within ± 8 days of either of the Follow-Up Visits (Visit 19 and Visit 20). Subjects who discontinue early from study drug are considered on study as long as they return for their regularly scheduled clinical efficacy visits as outlined above.

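### When randomization is delayed for infection, only the psychometric baseline is renewed; the lymphocyte baseline for the >33% reduction rule can be 35 to 38 days old at first dose and may date from the infection

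*Protocol*

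**What the plan says.** Criterion 20 (Section 9.3.2, and in near-identical terms in the Synopsis) excludes subjects with an active infection in the 4 weeks before randomization. It adds that "the timing of randomization can be extended (up to 4 weeks) to allow the infection to resolve" and that "psychometric tests conducted at Visit 2 (eg, MMSE, CDR) must be repeated". Under Duration of Treatment, the Synopsis repeats that in such subjects "the duration of the pre-randomization phase can be extended by up to 4 weeks".

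The ordinary timing is in Section 9.1.1: "All Screening Visit and Baseline Visit assessments must be completed within 50 days", then "a window of 7 to 10 days is to be observed between the completion of all Baseline Visit assessments and randomization".

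Table 6 schedules lymphocyte subsets at Screening and at Visit 2. In Table 7 the rows for blood count and lymphocyte subsets are blank at Visit 3 (Day 1, first dose) and begin at Visit 4 (Day 8). The only pre-dose repeat of these counts that the text requires is in criterion 22, to confirm a count below the LLN.

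Section 9.3.3(b) sends to weekly counts "Subjects with a >33% reduction from baseline in CD4 (T helper cells), CD8 (cytotoxic T cells), or CD19 (B cells) absolute counts". The same percentage reduction appears in Section 9.3.3(c), Table 1 and Table 2. In Table 2 it helps decide whether a subject with a moderate infection may stay on study drug or is discontinued.

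The Visit 3 notes in Tables 6 and 7 keep the 7-to-10-day interval "unless additional time is required to take Exclusion Criterion #19 into account". Criterion 19 concerns live vaccines and contains no extension.

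**The concern.** The protocol renews one part of the Visit 2 baseline after an infection delay and is silent on another part taken at the same visit. The silent part is the immune laboratory baseline, which feeds a rule that sites apply during the trial. It is therefore a protocol matter, not a detail that can wait for the statistical analysis plan.

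If an infection shifts a subset count and that count stays at or above the LLN, nothing in the text requires it to be redrawn, and it becomes the reference for the percentage rule. A baseline that is too low hides part of a real fall; one that is too high brings the trigger nearer with less drug effect. The subjects concerned have just had an infection, and immunological safety is part of a primary objective. For scale, Section 9.4.4 reports mean CD4 falls after 14 days of 3.1%, 22.9% and 17.3% at 100, 200 and 400 mg. A baseline shift of 10% to 30% would be of the same order as the larger of these.

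**Working it through.** **The protocol's own figure.** 50 days of assessments + the upper end of the 7-to-10-day window = 50 + 10 = 60 days. This matches Section 9.1.1: "Thus, the Prerandomization Phase will last for up to 60 days". With the infection delay the total is 60 + 28 = 88 days.

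**Age of the Visit 2 lymphocyte count at first dose.**
- Without delay: 7 to 10 days after completion of Visit 2.
- With the full 4-week delay: 7 + 28 = 35 to 10 + 28 = 38 days.
- This is not a strict ceiling. The window runs from completion of all baseline assessments, so blood drawn earlier in a Visit 2 spread over several days would be older.

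**Can the count date from the infection?** Put Visit 2 at day 0 and randomization at day 38. Four clear weeks back from day 38 is day 38 - 28 = 10. An infection active on day 0 and gone by day 10 therefore fits the rule.

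**Effect on the percentage rule.** Let U be the subject's usual count and s the relative shift in the recorded baseline, so the recorded baseline is U(1 + s). The rule is met when a later count falls below 0.67 × U(1 + s). The true fall needed is 1 - 0.67(1 + s). The documents give no value for s; the range below is assumed.

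| s (assumed) | True fall needed |
|---|---|
| -30% | 1 - 0.67 × 0.70 = 53.1% |
| -20% | 1 - 0.67 × 0.80 = 46.4% |
| -10% | 1 - 0.67 × 0.90 = 39.7% |
| 0 | 33.0% |
| +10% | 1 - 0.67 × 1.10 = 26.3% |
| +20% | 1 - 0.67 × 1.20 = 19.6% |
| +30% | 1 - 0.67 × 1.30 = 12.9% |

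A trigger with no true fall at all needs 0.67(1 + s) > 1, that is s above 1/0.67 - 1 = 49%, which is outside this range.

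**Illustration for CD4.** Appendix 5 gives a median of 805 cells/mm³ in this study's screened subjects and 404 as the LLN then in use (396 after its age adjustment). With a true baseline of 805 the rule is met below 0.67 × 805 = 539. With s = -30% the recorded baseline is 564, which is above the LLN and so not excluded, and the rule is met only below 378. Counts between 404 and 539 would have met the percentage rule against the true baseline. Against the recorded one they meet neither the percentage limb nor the LLN limb. For a moderate infection, Table 2 then puts the subject in a different row. Below 404 the LLN limb gives the same action whatever the baseline.

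**The case against.** Several points against the concern are fair.

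- **The infection may start after Visit 2.** The Visit 2 count is then older than usual but drawn before the infection. A reader might infer that the baseline of every delayed subject is distorted; the text supports only that it can be.
- **No source for the shift.** The documents do not say that infection moves CD4, CD8 or CD19, or by how much. The range above is an assumption. Nor do they say why the psychometric tests are repeated, so one cannot conclude that the protocol itself regards all Visit 2 data as invalid.
- **Other safeguards.** Criterion 22 excludes confirmed counts below the LLN, criterion 24 covers clinically significant laboratory deviations, and Section 9.5.2.2 allows extra samples at the investigator's discretion. What remains is a shifted count still within range.
- **Limited consequence.** A >33% reduction without infection leads to weekly counts and clinical judgment. The thresholds of 250, 150 and 50 cells/µL, the LLN limb, and discontinuation for severe infection, zoster or ocular herpes do not use baseline.
- **Treatment comparisons.** A reader might infer bias in the lymphocyte summaries between arms. The delay comes before randomization, so it gives no reason to expect a differential effect.
- **The cross-reference.** It is tempting to say that the schedule forbids the infection delay. The delay is stated in criterion 20 and in the Synopsis. Version 2.0 added a hepatic exclusion, now criterion 10, so the number in the tables may simply not have been updated.
- **Version.** The text is Version 3.0. Parts of a later version are present (Amendment 02 wording in Appendix 2, and Appendix 5), but not its criterion 20 or schedule. A later correction cannot be ruled out.

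These points limit the size of the problem. None supplies a required redraw or says which sample is baseline for Section 9.3.3.

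**Conclusion.** The point stands as an inconsistency of modest size in the Version 3.0 text. A site following the protocol exactly can apply the >33% reduction rule to a count that is 35 to 38 days old at first dose and may come from the infection that caused the delay, while the cognitive baseline from the same visit is renewed.

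The timing follows from the protocol's own intervals. The effect on the trigger (a true fall of 53% to 13% instead of 33%) rests on an assumed shift of -30% to +30%. The number of delayed subjects is unknown, so the overall impact cannot be estimated. The baseline-free thresholds and the LLN limb bound the harm to an individual subject.

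The mismatch between criterion 19 in the table notes and criterion 20 in the text needs no assumption.

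**What to change.** First check whether a version after 3.0 already deals with this. If not, reconcile criterion 20 (Section 9.3.2 and Synopsis), the Visit 3 notes of Tables 6 and 7, and Section 9.3.3, so that:

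- the immune laboratory baseline is handled consistently with the psychometric baseline when randomization is delayed for infection, for example by repeating the existing Visit 2 blood count, lymphocyte subset and immunoglobulin draw alongside the repeated psychometric tests;
- the protocol states which sample is the baseline for the percentage rule, and when any repeat falls relative to randomization;
- the criterion cited in the table notes and the criterion that contains the infection delay agree.

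The choice of sample and the clinical rules remain with the sponsor; no threshold or stopping rule needs to change for this point. The cost is amendment wording and, if the draw is repeated, 5 + 4 + 2 = 11 mL (Table 8) in delayed subjects only, who must already repeat the psychometric tests.

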9.3.2 Exclusion Criteria

Subjects who meet any of the following criteria will be excluded from this study:

1. Any neurological condition that may be contributing to cognitive impairment above and beyond that caused by the subject's AD pathology, including any co-morbidities detected by neurological examination or MRI
2. Modified Hachinski Ischemic Scale $>$ 4
3. History of transient ischemic attacks or stroke within 12 months of Screening
4. A history of epilepsy. Subjects with a history of seizures (not including a history of

simple febrile seizures in childhood) within 10 years of Screening. Subjects with disturbance likely to be due to seizures within 5 years of Screening.

5. Significant pathological findings on the brain MRI at Screening, including but not limited to: more than 4 microhemorrhages (defined as 10 mm or less at the greatest diameter), any microhemorrhage which is symptomatic, a single macrohemorrhage greater than 10 mm at greatest diameter, an area of superficial siderosis, evidence of vasogenic edema, greater than 3 lacunar infarcts or a single infarct >2 cubic centimeters involving a major vascular territory, evidence of severe microangiopathy, evidence of cerebral contusion, encephalomalacia, aneurysms, vascular malformations, infective lesions or space-occupying lesions (however, lesions diagnosed as arachnoid cysts and < 1cm in diameter at their greatest diameter need not be exclusionary) or brain tumors (eg, meningioma). (revised per Amendment 01)
6. Any psychiatric diagnosis or symptoms, (eg, hallucinations, major depression, or delusions) that could confound the MCI/Prodromal or mild to moderate AD diagnosis or could interfere with study assessments or procedures (revised per Amendment 01)
7. A score of ≥ 8 on the 15-item Geriatric Depression Scale (GDS) at Screening
8. Abnormally low serum vitamin B12 (<LLN) levels for the testing laboratory (if subject is taking vitamin B12 injections, level should be at or above the LLN for the testing laboratory) at Screening
9. Thyroid stimulating hormone above the normal range. Other tests of thyroid function with results outside the normal range should only be exclusionary if they are considered clinically significant by the investigator. This applies to all subjects regardless of whether or not they are taking thyroid supplements.

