22. CD4 (T helper cells), CD8 (cytotoxic T cells), or CD19 (B cells) absolute counts below LLN and confirmed by a repeat test conducted 1 week after the initial test
23. Ig (IgG, IgA, or IgM) levels below the LLN at Screening or Baseline, unless both the Investigator and the Medical Monitor agree that the finding is not clinically significant. The assessment of clinical significance will include, but not be limited to, evidence of clinical immunodeficiency. The discussion with the Medical Monitor should include a detailed review of medical history of infections, clinical and laboratory findings. (revised per Amendment 01)
24. Clinically significant deviation from normal in physical examination, vital signs, or clinically laboratory tests at Screening or Baseline
25. A prolonged QT/ corrected QT interval (QTc) interval (QTc >450 msec) at Screening or Baseline as demonstrated by average QTc interval from triplicate ECGs. A history of risk factors for torsade de pointes (eg, heart failure, hypokalemia, family history of long QT Syndrome) or the use of concomitant medications that prolong the QT/QTc interval.
26. Any other abnormality of the ECG at Screening or Baseline (including QRS >110 msec, abnormal electrical axis, PR interval >220 msec and conduction abnormalities) considered clinically significant by the investigator
27. Left bundle branch block at Screening or Baseline
28. Persistent heart rate <50 or >100 beats per minute (bpm) at Screening or Baseline
29. Persistent systolic blood pressure (BP) >165 mmHg or <90 mmHg and diastolic BP >100 mmHg or <60 mmHg at Screening
30. History of cardiac arrhythmias. Subjects with other heart diseases (eg, ischemic heart disease, clinically significant valvular heart disease) that are not stably and adequately controlled, or uncompensated heart failure (New York Heart Association Class III and Class IV)
31. Type 1 or Type 2 diabetes mellitus that is not well controlled

32. Malignant neoplasms within 5 years before Screening (except for basal or squamous cell carcinoma in situ of the skin, or localized prostate cancer that did not require systemic therapy; these do not exclude the subject). Subjects who had malignant neoplasms but who have had at least 5 years of documented evidence of no active disease before Screening need not be excluded.

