33. Medical conditions (eg, cardiac, respiratory, gastrointestinal, renal disease) that are not stably controlled, or which, in the opinion of the investigator(s), could affect the subject's safety or interfere with the study assessments
34. Hypopigmentation conditions (eg, albinism and vitiligo)
35. Known or suspected history of drug or alcohol dependency or abuse within 2 years before Screening, current use of recreational drugs or a positive urine drug test at Screening. Subjects who test positive in the urine drug screen need not be excluded if in the clinical opinion of the investigator, this is due to the subject taking prior/concomitant medications for a medical condition that is not exclusionary and not due to drug abuse.
36. Has a "yes" answer to the C-SSRS suicidal ideation questions 4 or 5, or any suicidal behavior assessment within 6 months before Screening, at Screening, or at the Baseline Visit; or has been hospitalized or treated for suicidal behavior in the past 5 years before Screening
37. Violations of the medical restrictions as specified in the Concomitant Medications section of the protocol
38. Planned surgery that requires general, spinal, or epidural anesthesia that would take place during the study. Planned surgery, which requires only local anesthesia and which can be undertaken as a day case without inpatient stay postoperatively, need not result in exclusion if in the opinion of the principal investigator this operation does not interfere with study procedures and subject safety.
39. Participation in any other interventional clinical study related to cognitive impairment within 6 months before Screening unless it can be documented that the subject was in a placebo treatment arm
40. Currently enrolled in another clinical study or used any investigational drug or device within 60 days or 5 half-lives of the investigational medication (whichever is longer) preceding informed consent
41. Hypersensitivity to the study drug or any of the excipients or to other BACE inhibitors, or to the PET tracer, or components of its formulation
42. Females who are lactating or pregnant (as documented by a positive beta-human chorionic gonadotropin [β -hCG] or human chorionic gonadotropin [hCG] test with a minimum sensitivity of 25 IU/L or equivalent units of β -hCG or hCG) at Screening or Baseline. A separate baseline assessment is required if a negative screening pregnancy test was obtained more than 72 hours before the first dose of study drug.

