43. Females of childbearing potential who:
 - Had unprotected sexual intercourse within 30 days before study entry or who do not agree to use a highly effective method of contraception (eg, total abstinence, an intrauterine device, a double-barrier method [such as condom plus diaphragm with spermicide], a contraceptive implant, an oral contraceptive, or have a vasectomized

partner with confirmed azoospermia) throughout the entire study treatment period or for-28 days after study drug discontinuation.

- Are currently abstinent, and do not agree to use a double-barrier method (as described above) or refrain from sexually active during the study treatment period or for 28 days after study drug discontinuation.
- Are using hormonal contraceptives but are not on a stable dose of the same hormonal contraceptive product for at least 4 weeks before dosing or who do not agree to use the same contraceptive during the study treatment period or for 28 days after study drug discontinuation.

(NOTE: All females will be considered to be of childbearing potential unless they are postmenopausal [amenorrheic for at least 12 consecutive months, in the appropriate age group, and without other known or suspected cause] or have been sterilized surgically [ie, bilateral tubal ligation, total hysterectomy, or bilateral oophorectomy, all with surgery at least 1 month before dosing]).

44. Males who have not had a successful vasectomy (confirmed azoospermia) or they and their female partners do not meet the criteria above (ie, not of childbearing potential or not practicing highly effective contraception throughout the study period or for 28 days after study drug discontinuation). No sperm donation is allowed during the study period and for 28 days after study drug discontinuation.

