11 PROCEDURES AND INSTRUCTIONS (ADMINISTRATIVE PROCEDURES)

11.1 Changes to the Protocol

Any change to the protocol requires a written protocol amendment or administrative change that must be approved by the sponsor before implementation. Amendments specifically affecting the safety of subjects, the scope of the investigation, or the scientific quality of the study require submission to health or regulatory authorities as well as additional approval by the applicable IRBs/IECs. These requirements should in no way prevent any immediate action from being taken by the investigator, or by the sponsor, in the interest of preserving the safety of all subjects included in the study. If the investigator determines that an immediate change to or deviation from the protocol is necessary for safety reasons to eliminate an immediate hazard to the subjects, the sponsor's medical monitor and the IRB/IEC for the site must be notified immediately. The sponsor must notify the health or regulatory authority as required per local regulations.

Protocol amendments that affect only administrative aspects of the study may not require submission to health or regulatory authority or the IRB/IEC, but the health or regulatory authority and IRB/IEC (or if regionally required the head of the medical institution) should be kept informed of such changes as required by local regulations. In these cases, the sponsor may be required to send a letter to the IRB/IEC and the Competent Authorities (or, if regionally required, the head of the medical institution) detailing such changes.

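### Exclusion criterion 29 joins its systolic and diastolic limits by *and*, so read literally one out-of-range pressure alone does not exclude; criterion 44 has a smaller slip of the same kind

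*Protocol*

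**What the plan says.** Section 9.3.2 opens with a rule that makes each item sufficient on its own: "Subjects who meet any of the following criteria will be excluded from this study".

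Criterion 29 reads "Persistent systolic blood pressure (BP) >165 mmHg or <90 mmHg and diastolic BP >100 mmHg or <60 mmHg at Screening". The Version 3.0 Synopsis has the same words, and so does the Version 2.0 Synopsis, so the wording passed through Amendment 01 unchanged.

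Two other criteria can reach a subject with abnormal blood pressure. Criterion 24 covers "Clinically significant deviation from normal in physical examination, vital signs, or clinically laboratory tests at Screening or Baseline". Criterion 33 covers medical conditions that are not stably controlled or that the investigator thinks could affect safety or the assessments. Neither gives a blood pressure value.

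Criterion 44 excludes "Males who have not had a successful vasectomy (confirmed azoospermia) or they and their female partners do not meet the criteria above", with those criteria glossed as "not of childbearing potential or not practicing highly effective contraception throughout the study period or for 28 days after study drug discontinuation". It ends: "No sperm donation is allowed during the study period and for 28 days after study drug discontinuation". The Synopsis carries the same first sentence.

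**The concern.** Criterion 29 is a numeric screening safety limit, and its purpose is to remove the decision from individual opinion. Two *or* pairs are linked by one *and* with no brackets. A site that takes the sentence at its word needs a systolic and a diastolic value both out of range. A site that takes it as two lists excludes on either. The same screened subject, say at 150/105, is then excluded at one site and left to the investigator at another. Stage B alone plans about 125 sites. Criterion 28, just before it, sets heart rate limits with a plain *or* and has no such problem.

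Criterion 44 joins having no vasectomy and failing the partner criteria by *or*, in a list where meeting any item excludes. A man without a vasectomy is then excluded whatever his partner's status. That defeats the contraception alternative in the same sentence, and the sperm-donation ban would have little purpose if only vasectomized men could enter.

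**Working it through.** The plan states no figure on this point, so there is none to reproduce. The check is an enumeration of patterns, not of subjects.

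**Criterion 29.** Inputs are the four limits in Section 9.3.2. Systolic has three states (<90, in range, >165) and diastolic has three (<60, in range, >100), giving 3 × 3 = 9 cells. Remove the one cell with both in range and the one that cannot occur (systolic <90 with diastolic >100, since diastolic would exceed systolic): 9 − 1 − 1 = 7. The example pressures are illustrative.

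| Example | Systolic | Diastolic | Both must be out | Either out |
|---|---|---|---|---|
| 190/110 | high | high | excluded | excluded |
| 180/55 | high | low | excluded | excluded |
| 85/50 | low | low | excluded | excluded |
| 190/85 | high | in range | not met | excluded |
| 150/105 | in range | high | not met | excluded |
| 110/55 | in range | low | not met | excluded |
| 85/65 | low | in range | not met | excluded |
| **Total excluded** | | | **3 of 7** | **7 of 7** |

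The two readings disagree on 7 − 3 = 4 patterns, namely every pattern in which only one pressure is abnormal.

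**Criterion 44.** Vasectomy (yes/no) by partner criteria (met/not met) gives 2 × 2 = 4 cells. One is essentially empty: criterion 43 counts a vasectomized partner with confirmed azoospermia as highly effective contraception, and criterion 44's own parenthesis limits the criteria in question to childbearing potential and highly effective contraception. A vasectomized man therefore meets them. That leaves 4 − 1 = 3:

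- vasectomy, criteria met: eligible as written and as intended;
- no vasectomy, criteria met: excluded as written, eligible as intended;
- no vasectomy, criteria not met: excluded both ways.

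As written, 2 of 3 are excluded; as evidently intended, 1 of 3.

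**Can the conjunctions be trusted elsewhere?** Not reliably. For the 28 days after dosing, the first bullet of criterion 43 has *and* in the Synopsis but *or* in Section 9.3.2. Criterion 44's sperm-donation sentence has *or* in the Synopsis but *and* in Section 9.3.2. A reader cannot recover intent from the conjunction alone.

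**The case against.** The strongest reply is that little harm can follow. Criterion 24 excludes clinically significant vital-sign deviations, and at Baseline as well as Screening, a wider window than criterion 29. Criterion 33 adds uncontrolled conditions. Table 7 schedules vital signs throughout treatment. Section 7.1 reports no clinically significant vital-sign changes in the single-dose study, and Section 9.4.4 says the same of 100 mg daily in Study 002. Many sites would read criterion 29 as meaning either pressure and would infer what criterion 44 intends. All of this lowers the stakes. It does not supply the number that criterion 29 was written to fix, because both backstops rest on judgment.

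Several stronger readings are tempting and are not supported:

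- **A third live reading of criterion 29.** Formal operator precedence gives systolic >165, or (systolic <90 and diastolic >100), or diastolic <60, which excludes 5 of 7. Its middle term is the impossible pattern, and no site would parse a clinical sentence that way. Pairing high with high and low with low would give 2 of 7. The practical ambiguity is joint versus either.
- **Unsafe subjects entering unchecked.** Criteria 24 and 33 still allow exclusion.
- **Men without a vasectomy actually shut out.** The intent can be recovered from the criterion itself, so no loss of subjects can be claimed.
- **Bias in the treatment comparison.** Eligibility is settled before double-blind randomization.
- **A defect known to persist.** Appendix 2, Listing 2, in the part of the document from a later version, cites Amendment 02. That version's exclusion list is not shown and may already be corrected.

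**Conclusion.** The point holds as a wording error in an operative eligibility rule of Version 3.0. On the literal reading criterion 29 captures 3 of 7 feasible out-of-range patterns; on the either-pressure reading it captures 7 of 7. The four patterns in dispute are the isolated abnormalities. Criterion 44 is a minor companion error: 2 of 3 feasible combinations excluded as written, against 1 of 3 intended.

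This rests on treating systolic <90 with diastolic >100 as impossible, and on accepting that a vasectomized man satisfies criterion 43's contraception list. The documents give no blood pressure distribution and no vasectomy rate, so the number of subjects affected cannot be estimated. The consequence is inconsistent eligibility and a softer screening safety limit. The endpoint, analysis and error rate are not affected. It is worth correcting because it changes a stated safety rule at little cost, but it does not justify an amendment of its own.

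**What to change.** First check whether Section 9.3.2 of the Amendment 02 version still carries the wording. If it does:

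- **Criterion 29:** *Persistent systolic BP >165 mmHg or <90 mmHg, or persistent diastolic BP >100 mmHg or <60 mmHg, at Screening.* The downside is that isolated low diastolic pressure, such as 110/55, then excludes. If the sponsor does not want that, it should say explicitly which rule it means; either choice removes the ambiguity.
- **Criterion 44, first sentence:** *Males without a successful vasectomy (confirmed azoospermia), unless they and their female partners meet the criteria above (ie, the partner is not of childbearing potential, or highly effective contraception is practiced throughout the study period and for 28 days after study drug discontinuation).* Leave the sperm-donation sentence in Section 9.3.2 as it is.
- **Synopsis:** align both criteria with Section 9.3.2.

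The cost is two sentences in Section 9.3.2 and the same two in the Synopsis. Section 11.1 says "Amendments specifically affecting the safety of subjects, the scope of the investigation, or the scientific quality of the study require submission" to authorities and further IRB/IEC approval, so the changes should travel with the next planned amendment. If Amendment 02 has already corrected the text, nothing is needed.
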